6 STATISTICAL METHODS

In the following section we will describe the general statistical methodology to be used for the analysis of endpoints described in Table 1.

6.1 Covariate Adjustment

Unless otherwise stated below, where feasible the following covariates will be incorporated in analysis models for all endpoints described in Table 1.

- 1. Study Arm (intervention, usual care) ITT Phase 1 analyses only
- 2. Study Phase (sustainability, intervention) ITT Phase 2 sustainability analyses only
- 3. Study Phase (intervention, usual care) ITT Phase 2 effectiveness analyses only
- 4. Race (non-white; white)
- 5. Age (degree two polynomial)
- 6. Index hospitalization diagnosis (stroke; TIA)
- 7. NIH Stroke Scale (NIHSS) Score category (0, 1-4, 5-15, and 16-42) categories may be collapsed to 5-42 due to sample size requirements.
- 8. Sex (female; male)
- 9. Prior stroke
- 10. Prior TIA

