Appendix 39 – Consent Matrix	193

Background

Stroke is the fifth-leading cause of death in the United States (US) and a major cause of long-term disability. North Carolina (NC) is in the Stroke Belt, a region of the US with a very high stroke incidence. Eastern NC is the "buckle" of the Stroke Belt, where stroke mortality is 40% higher than the US average and hospital admission rates are the highest in NC. African Americans, over 20% of the population in NC, are more likely than their white counterparts to die of stroke at relatively young ages. There is also evidence that African-Americans are more likely to be readmitted after stroke.

Stroke exemplifies a complex co-morbidity condition, with 85% of Medicare beneficiaries with stroke having four or more other chronic health conditions,⁴ and their health care is costly. Stroke patients with congestive heart failure have per capita costs that are about five times higher than the average spending for Medicare fee-for-service beneficiaries.⁴ In addition, stroke patients are frequently readmitted to the hospital.^{5,6} A PCORI-funded study shows that 25% of stroke patients discharged home without post-acute care are readmitted within 90 days⁷. These data align with what stroke survivors and caregiver advocates from across NC have said that stroke patients need. One of our patient partners who started a support group for other stroke survivors stated:

"You can't just place an individual back in their home with a bottle of pills and a follow-up visit...There is a real need for assistance when patients get home...What is in place for the patient? Nothing... No visiting nurse, no one to answer questions, or help them get what they need. That is why people end up back in the hospital."

Roughly half of stroke patients in NC are discharged directly home, often with new disability. Around 44% cannot walk independently at discharge. Complications from immobility account for up to 51% of deaths in the first 30 days after ischemic stroke. Other complications are common early after stroke and include falls and fractures, aspiration pneumonia, deep vein thrombosis, infections, depression, and adverse events associated with warfarin therapy. 11–16 Even those with mild post-stroke disability can have physical and cognitive deficits which often go undetected during acute hospitalization. These mild disabilities interfere with function, and management of risk factors and medication. 17,18

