Secondary Outcome	Cognition	MOntreal Cognitive Assessment (MOCA) Mini	@90 days, consenting patients asked by CSRL	24
Secondary Outcome	Medication Adherence	4-item Morisky Green-Levine Scale	@90 days, consenting patients asked by CSRL	24
Secondary Outcome	Secondary Prevention Self-Monitoring of BP	By asking: "Do you check your blood pressure at home?"	@90 days, consenting patients asked by CSRL	24
Secondary Outcome	Blood Pressure Management Effectiveness	For those who check BP at home, we ask: "Is your blood pressure less than 140/90 most of the time?"	@90 days, consenting patients asked by CSRL	24
Secondary Outcome	Falls and Hospitalization*	Questions to capture: Number of falls, injuries, and hospitalizations *Note: Note: Outcome is binary variable of Fall either Yes or No. Hospitalizations, injuries and number of falls were collected but were not used in the analyses	@90 days, consenting patients asked by CSRL	24

Secondary Outcome	Fatigue	PROMIS Fatigue Instrument – Adult Short Form 4A	@90 days, consenting patients asked by CSRL	24
Secondary Outcome	Satisfaction with care	Questions on how the patient felt about care and treatment from health care providers.	@90 days, consenting patients asked by CSRL	24
Exploratory Aim	Use of Community Resources	By asking: "Since discharge from the hospital, have you used services such as Senior Services, Meals on Wheels, in-home aides, or stroke survivor or caregiver support groups?"	@90 days, consenting patients asked by CSRL	24
Data collected to support the operations of the trial.	Initial Presentation Data	Hospital arrival and Mode of arrival, Ambulatory status prior to admission, Diagnosis at admission, NIHSS, Imaging performed, etc.	Entered into the COMPASS Database by the hospital	9
Data collected to support the operations of the trial.	Demographic Data	DOB, Race, Gender, Insurance, Medical History, Medication, etc.	Entered into the COMPASS Database by the hospital	9
Data collected to support the operations of the trial.	t-PA Data	Time t-PA was initiated, BP and Glucose levels, bleeding complications, etc.	Entered into the COMPASS Database by the hospital	9
Data collected to support the operations of the trial.	In-hospital Data	Admission data, secondary prevention counseling, treatment, lipid profile, medications, treatments, etc.	Entered into the COMPASS Database by the hospital	9

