Тур	e: 🗆 Home 🗆 Mobile 🗆 Work	□ Other	
c. Alternate Mailir	ng Address		
	Address Line 1		
	Address Line O		
	Address Line 2		
	City	State	Zip
15. Relationship to p	patient?		
	 □ Spouse (husband or wife) □ Sibling □ Son or daughter □ Friend or neighbor □ Parent or legal guardian □ Other, specify: 		
D DEMOCRAPHIC	S AND IN-HOSPITAL DATA		

☐ Asian☐ American☐ Native HI): rican American Indian / Alaska Native / Other Pacific Islander	
18. Hispanic ethnicity: ☐ Yes	□ No	
☐ Medicare	Supplemental Insurance / Med surance npus / other	ligap
20. Does the patient have documented	ed past medical history of the f	ollowing (check all that apply):
☐ Stroke☐ Transient ischemic attack	☐ Hypertension☐ Dyslipidemia	☐ Chronic renal insufficiency☐ Heart Valve☐ Current pregnancy or within 6
 □ Atrial Fibrillation or Flutter □ Myocardial infarction or CAD □ Congestive heart failure □ Carotid stenosis □ Peripheral arterial disease 	 ☐ Smoking ☐ Depression ☐ Drug/alcohol abuse ☐ Family history of stroke ☐ Migraines 	weeks post-partum Hormone replacement therapy Sickle cell Sleep apnea Diabetes mellitus
21. Please enter the body mass inde	x (BMI) kg/m²	□ Not documented
22. What was the patient's ambulator	ry status prior to admission ?	
		vithout a device)
23. Initial NIH Stroke Scale Score (00)-42)	Not documented
25. Did the initial exam show aphasia	a? ☐ Yes ☐ No / not do	ocumented
26. Hospital admission date for this e	event: / /	/
☐ No admission date; patient was	not admitted as an inpatient (s	select reason below)
	lirectly from ED to home rom observation status without	inpatient admission

2/a. If YES	S, check all that apply:	
☐ Hom	e health Physical Therapy e health Occupational Therapy e health Speech Therapy Outpatient Physical Therapy Outpatient Occupational Therapy Outpatient Speech Therapy	
27b. If NO	indicate why not	
☐ Patie	nt not evaluated for need of rehab services nt not in need of rehab services nt / family refused r reason	
28. What w	as the patient's ambulatory status at discharge?	
	 □ Able to ambulate independently (with or without a device) □ With assistance (from person) □ Unable to ambulate □ Not documented 	
30. Hospita	I discharge date:	
	ollow-up clinic visit with a nurse, nurse practitioner, or physician assistant (i.e. p nal care clinic, neurologist, or other doctor visit) scheduled prior to discharge?	rimary care,
	☐ Yes → Fill in type and date below	
31a	☐ No If YES, check all visit types that apply and enter the date (if known)	

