6.1.1 Sensitivity to Covariate Adjustment

Where feasible, we will also perform analysis using different covariate sets that includes as possible adjustment variables the set above as well as other covariates. These additional covariates include but are not limited to:

- 1) Whether the patient lives in a rural or urban area (based on RUCA codes)
- 2) Whether the hospital is in a rural or urban area (based on RUCA codes)
- 3) Whether the patient had a rehabilitation referral at discharge (physical therapy, occupational therapy, or speech therapy)
- 4) Whether the patient had a home health referral at discharge
- 5) Whether the patient had a documented PCP in their medical record
- 6) Dual eligibility for Medicaid (FFS analyses only)
- 7) History of depression
- 8) History of hypertension
- 9) History of smoking
- 10) History of CVD comorbidities

Covariates listed above will be ascertained as part of the COMPASS study and not from claims. Variables will be selected for inclusion in the sensitivity analysis model using a backward selection procedure that accounts for missing covariate data using methods described in Section 6.5. The sensitivity model will include key clinical covariates as well as any of the above variables that have a p-value > 0.10 (unadjusted for multiple comparisons). Estimates of treatment effects will be produced for each step in the model selection procedure to understand how effect estimates change based on different adjustment sets.

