6.2 Analysis of Binary Endpoints

The set of binary endpoints to which this section pertains are given as follows:

1. Incidence of 30-day all cause readmissions

- 2. Incidence of 90-day all cause readmissions
- 3. Use of TCM billing codes

For the analysis of 30- and 90-day all cause readmissions, patients who have continuous coverage over the 30- or 90-day reference period will be included in the analysis. For analysis of TCM billing codes, patients who have continuous coverage over the 30-day period following discharge from the index hospitalization will be included in the analysis. The percentage of patients with incomplete coverage over the 90-day period following discharge from the index hospitalization is expected to be low. In the event that more than 10% of the patients linked to claims data have incomplete coverage over the relevant 30- or 90-day reference period, we will assess the robustness of any important findings to exclusion of these patients from analyses using techniques such as multiple imputation from a time-to-event model that accounts for the observed follow-up period for patients who drop out of coverages during the relevant reference period.

For readmission endpoints, patients who die prior to the end of the reference period without a qualifying readmission will be treated as not having a readmission. Prior analyses of 90-day mortality based on the full COMPASS cohort has demonstrated that the percentage of patients who die within 90 days of discharge from the index hospitalization is approximately 2.0% and did not differ by treatment arm.⁴ Thus, the impact of excluding patients who did not survive for the entire reference period is not expected to strongly influence results. Nonetheless, in the event that more than 5% of the patients linked to claims data die within the reference period, we will assess the robustness of any important findings by performing a sensitivity analyses that includes these patients as having met the endpoint for all cause readmissions.

For all binary endpoints, we will employ generalized linear mixed models (GLMM) with a logistic link function. Models will include a hospital-specific random effect, and adjust for the covariates described in Section 6.1.

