6.3 Analysis of Time-to-Event Endpoints

6.3.1 One-Year Mortality Analysis

Analysis of the one-year mortality endpoint will be performed using a Cox proportional hazards model that adjusts for the covariates described in Section 6.1. Analyses will be performed using the method of Wei, et al.⁵ which models the marginal distribution for event times and account for correlation between event times within a hospital unit through use of a robust sandwich variance estimator for model parameters.

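### The main claims models omit comorbidity beyond prior stroke/TIA, pre-admission walking status and, in FFS Medicare, dual eligibility; this matters most for the Phase 2 versus Phase 1 contrasts

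*SAP*

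**What the plan says.** SAP Section 6.1 opens: "Unless otherwise stated below, where feasible the following covariates will be incorporated in analysis models for all endpoints described in Table 1". Apart from arm or phase, the list holds race, age (quadratic), index diagnosis, NIHSS category, sex, prior stroke and prior TIA. Prior disease enters only through "9. Prior stroke" and the TIA item after it.

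Later sections apply this list without adding to it. For readmission and TCM billing, Section 6.2 says: "Models will include a hospital-specific random effect, and adjust for the covariates described in Section 6.1". For death, Section 6.3.1 specifies a "Cox proportional hazards model that adjusts for the covariates described in Section 6.1".

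Section 6.1.1 describes a sensitivity model, to be fitted where feasible and built by backward selection. Its candidates include "Dual eligibility for Medicaid (FFS analyses only", depression, hypertension, smoking and an undefined group of CVD comorbidities. The list is expressly open-ended, and the treatment effect is to be reported at each selection step. Walking status, diabetes and renal disease are not named.

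The omitted items are collected:
- The protocol's outcome table records "Ambulatory status prior to admission, Diagnosis at admission, NIHSS" at presentation.
- Item 20 of the Enrollment Form in both phases lists "Congestive heart failure" with atrial fibrillation, coronary disease, peripheral arterial disease, diabetes and renal insufficiency.
- Item 22 of both forms records ambulation before admission.
- Section 6.1.1 says its covariates, dual eligibility included, come from study data rather than claims.

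**The concern.** The endpoints are all-cause readmission, ED use, SNF/IRF entry and death. Comorbidity and pre-stroke function plausibly predict all of these. The protocol's Background points the same way: it says 85% of Medicare beneficiaries with stroke have four or more other chronic conditions, and adds: "Stroke patients with congestive heart failure have per capita costs that are about five times higher than the average spending for Medicare fee-for-service beneficiaries". That second statement is about cost, so it supports the argument only indirectly.

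Two comparisons depend on the same list, and they are exposed differently:
- **Phase 1** compares 20 with 20 randomized units. Randomization was stratified on hospital volume and stroke-center status only. The protocol's Analytical Plan accepts that patient-level imbalance may occur.
- **Phase 2** (SAP Section 5.2) compares one phase with another in hospitals that delivered the intervention. Enrollment ran from June 2016 to March 2018 in Phase 1 and from November 2017 to January 2019 in Phase 2. If the mix of comorbidity, prior function or dual eligibility changed between those periods, nothing in the main model corrects for it except correlation with the listed covariates. A systematic shift of that kind is not reflected in the confidence interval.

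**Working it through.** The SAP attaches no sample size, event count or power to the covariate set, so there is no plan figure to reproduce. The 20 versus 20 units come from the protocol. Prevalence *p*, ICC, FFS patients per unit *m*, the factor's hazard ratio (HR), drift *d*, stratum sizes and death rates are all assumed.

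**Phase 1, chance imbalance in one omitted binary factor**

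SD of the arm difference = √{2p(1−p)[1+(m−1)ICC]/(20m)}

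Shift in the treatment ratio for imbalance δ = [1+(HR−1)(p+δ)]/[1+(HR−1)p]

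- Low end, p=0.08, ICC=0.02, m=75: √(0.1472×2.48/1500) = 0.0156. With HR 2: 1.0956/1.08 = 1.014.
- High end, p=0.15, ICC=0.03, m=50: √(0.255×2.47/1000) = 0.0251. With HR 3: 1.3502/1.30 = 1.039.

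The SD is therefore 1.6 to 2.5 percentage points. One SD shifts the ratio by 1.4% to 3.9%, and two SD by 2.9% to 7.7%.

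A second set of assumptions (p 10–30%, ICC 0.01–0.10, m 50–150, HR 1.5–2.0) gives 2.4 to 9.8 points at 1.96 SD, and a shift of about 1% to 7.5%.

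**Phase 2, drift between phases**

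The 20-versus-20 SD does not apply, because the same hospitals appear in both phases. Only the shift formula carries over, with d in place of δ. With p=0.20:
- d=0.03, HR 1.5: 1.115/1.10 = 1.014
- d=0.10, HR 2.0: 1.30/1.20 = 1.083

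The documents give no estimate of actual drift.

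Both calculations treat the factor as independent of the adjusted covariates. Correlation with age, NIHSS or prior stroke would shrink the shift; several factors moving in the same direction would enlarge it.

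**Cost in parameters**

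The Section 6.1 model uses 11 df: arm or phase 1, race 1, age 2, diagnosis 1, NIHSS 3, sex 1, prior stroke 1, prior TIA 1.

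| Model | df | Deaths per parameter, N=2,000, 5–10% dead (100–200 deaths) |
|---|---|---|
| Section 6.1 as written | 11 | 9.1–18.2 |
| + walking status (2), count (1), dual (1) | 15 | 6.7–13.3 |
| + walking status (2), five diseases (5), dual (1) | 19 | 5.3–10.5 |

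In an assumed 300-patient payer stratum (15–30 deaths), the existing model already has only 1.4–2.7 deaths per parameter. Adding walking status and a count (14 df) gives 1.1–2.1.

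Readmission has more room. At the 25% 90-day rate that the Background gives for patients discharged home without post-acute care, 2,000 patients yield 500 events, or 500/19 ≈ 26 per parameter even with the fullest set.

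**The case against.** **Section 6.1.1 already goes part of the way.** It includes dual eligibility, and its CVD group plausibly covers heart failure, atrial fibrillation, coronary disease and peripheral arterial disease. Because estimates are reported at each step and backward selection normally starts from the full model, a result adjusted for all listed candidates should appear. This stands, so a reader who infers that these factors are never adjusted for goes too far. The safeguard is still weak: it is conditional on feasibility and data-driven. Read literally, its rule also keeps variables with p-values above 0.10, the reverse of usual practice.

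**Phase 1 is randomized.** Chance imbalance is part of sampling variation, which the hospital random effect or the sandwich variance is there to carry. This stands. With 2,000 to 3,000 FFS patients (50–75 × 40) and an assumed 10–25% event rate, there are 200 to 750 events and SE(log HR) ≈ 2/√events = 0.07 to 0.14 before clustering. A one-SD shift is then roughly 0.1 to 0.5 SE. A reader might also suspect recruitment imbalance, because site staff enroll after randomization. The documents give no figure for it, and they limit it through daily screening, no hospital consent and retrospective enrollment of missed patients.

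**Insurance status.** Protocol Secondary Aim 5 promises adjustment for insurance status, so a reader might infer a breach. The documents do not support that: SAP Section 5.1 stratifies every analysis by payer, which reasonably meets the aim, and the aim does not mention dual eligibility.

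**Sparse models and timing.** Extra covariates strain the mortality and small-payer models and change the conditional odds or hazard ratio. The addendum also cites the published trial results, so a late change could look post hoc. Its parent Phase 1 SAP, not among the documents reviewed, may explain the list. These points shape the fix but do not remove the need for it.

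**Conclusion.** The point holds in limited form. The main claims models omit baseline factors that the study collects and that plausibly predict the endpoints, and the sensitivity step only partly makes up for this.

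For Phase 1 the consequence is some lost precision and less protection against chance imbalance. The shift of 1.4% to 3.9% per factor at one SD is an illustration resting on assumed prevalence, ICC, cluster size and HR. It does not show the analysis to be biased or invalid.

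For the Phase 2 versus Phase 1 contrasts the case is stronger in kind: randomization gives no protection, and drift in these factors would pass into the main estimate. The 1.4% to 8.3% range is conditional on a drift that the documents neither report nor rule out. The Phase 1 imbalance figures should not be carried over to Phase 2.

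**What to change.** Add the following to Section 6.1, at least for readmission, mortality and all Phase 2 contrasts:
- Walking status before admission (Enrollment Form item 22).
- A comorbidity count or short set from item 20: heart failure, atrial fibrillation, coronary disease, diabetes and chronic renal insufficiency.
- Dual eligibility, in FFS models only, since the Medicaid and BCBSNC sets exclude Medicare enrollees.

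Use the count rather than separate indicators for mortality and in the Medicaid and BCBSNC strata. State in advance any reduced set for cells with few events. Take the items from the Enrollment Form, because the Stroke Care Card is optional in Phase 2. Impute missing values with the MICE procedure already planned in Section 6.4.

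Do not move the discharge rehabilitation and home-health referrals from 6.1.1 into the main set without justification: they follow hospital randomization and could be affected by arm. While editing 6.1.1, correct the direction of its p-value rule and its pointer to Section 6.5 for missing-data methods, which are in 6.4. To answer any charge of a post hoc change, record when and why the list was extended, and report the current 6.1 model alongside.

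The cost is SAP wording, no new data, 4 to 8 more parameters in FFS models (3 with the count in the other strata), and a slightly different conditional odds or hazard ratio.

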Since the primary endpoint (SIS-16) is measured on a continuous scale, we will use a mixed model to compare the COMPASS and control groups. Although the stratified randomization of hospitals should balance most important hospital-level characteristics between groups, since imbalances may exist between groups on patient-level characteristics, we propose to include both fixed and random effects in this mixed model. The first model will include two fixed effects: stratum (1 to 6) and the intervention effect (COMPASS vs. control) and one random effect: hospital. This additive model can be written as: $Y_{ijk} = \mu + \gamma_k + \alpha_j + \beta_{k(j)} + \epsilon_{i(jk)}$, where Y_{ijk} is the outcome (i.e. SIS at 90 days) measured on the i^{th} patient, under the j^{th} intervention (j=1 (COMPASS), 2(Control) in the k^{th} hospital; μ is the grand mean; γ_k is the stratum (1 to 6) for hospital k; α_j is the fixed treatment effect for group j (COMPASS/CNT); $\beta_{k(j)}$ is the random effect of the k^{th} hospital nested within the exposure group; and $\epsilon_{i(jk)}$ is the error term for the i^{th} patient nested within the treatment group and hospital. Other fixed effects can be added at the patient level (e.g. age, gender, race, stroke severity, or SES) for sensitivity analyses. The random hospital effect allows the possibility of correlated observations (patients) within hospitals. Of primary interest is the treatment effect (α_i), which indicates difference in the dependent variable (SIS-16) between groups.

After we fit our primary model, we will consider other models that may include more patient-level and hospital-level characteristics. For instance, since some patients may be transferred to a different hospital before being discharged home, we can include a yes/no variable on that point. Although hospitals will be stratified pre-randomization based on stroke volume, we can include a hospital-level covariate for the total number of stroke patients discharged home for each hospital. With 40 clusters (of the 41 hospitals, 2 were randomized together) included, we will be able to add other cluster-level covariates to the model if needed.

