For secondary aims and outcomes measured on a continuous scale, we will use a similar approach as above (i.e. for the Modified CSI). For binary outcomes such as whether a patient is readmitted within 30 or 90 days (Secondary Aim 2), we will use mixed logit models to fit the relationship between the intervention and outcome measures. The mixed logit model is similar to the mixed model presented above but uses a logit link in a generalized linear mixed model. Software is

Application - IRB00035998

readily available (e.g., SAS PROC GLIMMIX) that can fit these models. The mixed logit model approach will also allow a mixture of fixed and random effects to be included as in the mixed model above. Other Secondary Aim 2 variables will be analyzed using a mixed model or alternatively generalized linear mixed models (e.g., Poisson regression [with overdispersion] for the number of inpatient days).

We will examine 1-year mortality rates as a binary outcome and use the methods described above to compare groups, but we will also consider mortality as a time-to-event outcome and compare groups using Cox proportional hazards models. In these survival analysis models, the treatment indicator will be included as the primary independent variable and the stratum included as stratification factor.

Human Subjects Protection

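### The claims SAP leaves the randomisation strata out of its main Phase 1 models, contrary to the protocol's mortality model and, by reference, its readmission model

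*SAP*

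**What the plan says.** The protocol (Randomization; Analytical Plan) randomises 40 units from 41 hospitals in permuted blocks of two. The six strata cross three levels of annual stroke volume with primary stroke center (PSC) status.

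The protocol's models carry the strata as follows:

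- Base mixed model: "The first model will include two fixed effects: stratum (1 to 6) and the intervention effect", with hospital as a random effect. Patient covariates are secondary: "Other fixed effects can be added at the patient level (e.g. age, gender, race, stroke severity, or SES) for sensitivity analyses". With 40 clusters "included, we will be able to add other cluster-level covariates to the model if needed".
- Readmission at 30 and 90 days: "The mixed logit model is similar to the mixed model presented above but uses a logit link in a generalized linear mixed model".
- One-year mortality as a survival outcome: "the treatment indicator will be included as the primary independent variable and the stratum included as stratification factor". The protocol presents this as a further analysis, alongside mortality as a binary outcome.

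The SAP addendum fixes one covariate set in 6.1: "where feasible the following covariates will be incorporated in analysis models for all endpoints described in Table 1". It contains arm or phase, race, age, index diagnosis, NIHSS, sex, prior stroke and prior TIA. The model sections refer back to it:

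- 6.2, binary endpoints: "Models will include a hospital-specific random effect, and adjust for the covariates described in Section 6.1".
- 6.3.1, mortality: "Analysis of the one-year mortality endpoint will be performed using a Cox proportional hazards model that adjusts for the covariates described in Section 6.1", with a hospital-level sandwich variance.

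The only planned stratification is by insurer (SAP 5.1). The extra covariates in SAP 6.1.1 are for sensitivity analyses. That list is declared non-exhaustive and is subject to selection by p-value. It names hospital rural or urban location, but not stroke volume or PSC status.

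**The concern.** Two documents of about the same date (the protocol pages are dated 19 March 2021; the SAP's web references were accessed 15 February 2021) specify different models for the same endpoints. The addendum gives no reason.

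Blocking within strata balances them across arms, so stratum differences are largely removed from the treatment contrast. A model without stratum terms still counts those differences as between-hospital noise. If volume and PSC status predict the outcome, reported standard errors are then too wide and tests too conservative.

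It should also be on record which mortality model is the prespecified one, because SAP 6.2 already reports a comparison of 90-day mortality by arm.

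**Working it through.** **Contradiction by endpoint**

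| Endpoint | Protocol | SAP | Status |
|---|---|---|---|
| One-year mortality (Cox) | stratum as stratification factor | 6.1 list only | express conflict |
| 30- and 90-day readmission | similar to a model with stratum fixed effects | 6.1 list plus hospital random effect | conflict by reference |
| Other Table 1 endpoints, Phase 1 | no stratified model stated | 6.1 list | departs from the design only |

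The proviso in SAP 6.1 for exceptions stated later does not help, since 6.2 and 6.3.1 point back to 6.1.

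**Size: closed form**

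Neither document gives a standard error or ICC for these endpoints, so there is no planned figure to reproduce. Let ρ be the ICC, m the analysed patients per unit and s the share of between-hospital variance explained by strata. With equal clusters and strata balanced by design:

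- variance that the model without strata reports ∝ ρ + (1−ρ)/m
- true variance ∝ (1−s)ρ + (1−ρ)/m
- ratio of reported to true SE = square root of the quotient

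Example with ρ = 0.05, m = 60, s = 0.50: reported 0.05 + 0.95/60 = 0.0658; true 0.025 + 0.0158 = 0.0408; ratio √(0.0658/0.0408) = 1.27. With s = 0.25: √(0.0658/0.0533) = 1.11. With s = 0 the ratio is 1.

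**Size: simulation under no treatment effect**

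Assumptions: 40 units, strata of 4-10 units, blocks of two, and 10, 30 or 60 patients per unit. All payers together average 6,000/40 = 150, but the analyses are by payer. Readmission is a logistic GLMM with about 20% events. The 25%, ICC 0.05 row comes from a smaller run (800 trials, no patient covariate) at 30 and 60 per unit only.

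| s | ICC | Closed form (10/30/60) | Simulated SE ratio | Test size at nominal 5% |
|---|---|---|---|---|
| 50% | 0.02 | 1.05 / 1.11 / 1.17 | 1.05 / 1.10 / 1.16 | 4.4 / 3.4 / 2.5% |
| 50% | 0.05 | 1.10 / 1.20 / 1.27 | 1.08 / 1.18 / 1.23 | 3.8 / 2.5 / 1.7% |
| 25% | 0.02 | 1.02 / 1.05 / 1.08 | 1.00-1.05 | 3.8-5.0% |
| 25% | 0.05 | 1.05 / 1.09 / 1.11 | – / 1.07 / 1.13 | – |

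If a patient covariate in the model carries half of the stratum effect, the readmission ratio falls to 0.99-1.02 (ICC 0.02) or 1.02-1.05 (ICC 0.05).

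**Mortality**

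The 2.0% at 90 days in SAP 6.2 extrapolates, at constant hazard, to 1 − 0.98^(365/90) = 7.9% at one year. With 6% and 8% assumed, log-hazard variance 0.10 between hospitals and s = 50%, the ratios are 0.97 / 1.01 / 1.04 and 0.99 / 1.03 / 1.06.

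**Second simulation**

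This used unequal cluster sizes, residual hospital SD 0.15, 25% readmission and 7% mortality, with 2,400 and 6,000 patients.

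| Stratum SD | Implied s | Readmission ratio | Mortality ratio |
|---|---|---|---|
| 0 | 0 | 0.94, 0.94 | 0.91, 0.95 |
| 0.1 | 0.01/0.0325 = 31% | 0.99, 1.03 | 0.93, 0.94 |
| 0.2 | 0.04/0.0625 = 64% | 1.10, 1.24 | 1.04, 1.03 |
| 0.4 | 0.16/0.1825 = 88% | 1.51, 1.79 | 1.24, 1.44 |

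**Precision of the estimate**

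At 60 per unit and s = 50%, the true SD without and with strata was 0.129 and 0.129 (GLMM), and 0.181 and 0.181 (Cox, 6% events). Only the reported error changes.

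**Effect of adding strata without a correction**

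Cox with six strata and an uncorrected sandwich had test size 7.1-9.8% in the first simulation and 10.3-12.2% in the second. With a G/(G−k) variance correction and t reference it was 3.6-5.7% (six strata) or 3.0-5.5% (main effects), in the first simulation. The GLMM with volume and PSC main effects went from 4.8-7.4% by z to 4.1-6.3% by t. With six strata and unequal clusters it was 7.4-10.9% by z and still 6.4-9.8% by t on 33 df.

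**The case against.** The strongest reply has five parts.

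- The only express conflict is mortality, where the effect is negligible under modest stratum effects, and the protocol offers that Cox model as an additional analysis. For readmission the strata enter only through a cross-reference. This stands, and it limits the weight of the point.
- The protocol's Secondary Aim 5 asks for adjustment for race, sex, age, stroke severity and insurance status in all outcomes. The SAP's list plus stratification by payer delivers that. This also stands: the patient covariates are not at issue. But Aim 5 does not withdraw the stratum terms in the Analytical Plan.
- The open sensitivity list in SAP 6.1.1 could admit the strata. It could, but it does not prespecify them, and it does not govern the main models.
- The document is an addendum, and the parent Phase 1 SAP, which may give a reason, was not supplied. That is a real limit. The addendum cites the parent for study design and missing-data detail, while 6.1 sets its own covariate list.
- Restoring the protocol text alone would worsen calibration. The test sizes above confirm this, and it shapes the fix.

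A reader might infer from the earlier 90-day mortality comparison that the model was chosen after seeing results. The documents do not show this. SAP 6.2 reports that 90-day mortality did not differ by arm, SAP 6.3.1 does put a mortality model on record, and dropping strata leans towards the null.

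**Conclusion.** The omission is real and should be corrected or explained for the Phase 1 mortality and readmission models. For the other Phase 1 endpoints it is a departure from the stratified design, not a contradiction. The Phase 2 comparisons set the same hospitals against themselves across phases and are outside this point.

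Only the direction is firm: reported standard errors are larger than those from a stratum-adjusted model. For readmission they exceed the true SE by roughly 0-13% at a 25% stratum share and by up to about 23% at 50% (ICC 0.05, 60 per unit). Larger shares or clusters would give more. Two things pull the figure down. Patient covariates may absorb part of the stratum effect. Also, ICC 0.05 at a 20% rate is a strong assumption: the logit SD is √(0.05/0.16) = 0.56, which spreads 95% of hospitals over about 8% to 43%.

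Three stronger readings are not supported. The omission does not bias the treatment effect, because the strata are balanced by design. It does not make the estimate less precise. And it does not mean that the SAP's tests are conservative overall: with 40 clusters, no small-sample correction and non-prognostic strata, test size was about 5.6-8.6% in the simulations without stratum terms.

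**What to change.** For Phase 1 only:

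- Add stroke volume (three levels) and PSC status (yes/no) to SAP 6.1. Use them as fixed effects in the GLMM, and as main effects or stratification factors in the Cox and PWP models. Prefer main effects (3 df) where a payer subset is small, particularly for PWP, which already splits its risk sets by event order.
- Reconcile SAP 6.2 and 6.3.1 with the protocol's Analytical Plan. If the strata are left out on purpose, state the reason.
- Pair the strata with a finite-cluster correction. For the GLMM use t-based degrees of freedom, for example 40 − 2 − 3 = 35 with main effects. For Cox and PWP use a bias-corrected sandwich with a t reference, for example 40 − 7 = 33 df with six strata or 35 with main effects. Carry the correction through the pooling over 100 imputed datasets. Since t alone did not restore 5% in the unequal-cluster runs with six strata, check the chosen method by simulation at the actual cluster sizes.
- Name the randomised unit (40) as the cluster, and state that odds and hazard ratios are conditional on stratum.

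Both factors are already known for every site, so no new data are needed. The cost is a few degrees of freedom, some specification and programming, and estimates that are conditional on stratum.
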